	
 
• History of an allogeneic hematopoietic cell transplant for any hematologic disorder with any conditioning regimen, donor, or graft source.
 
• Need for systemic treatment for chronic GVHD.
 
• No previous systemic treatment for chronic GVHD.
 
• Prior ECP for the treatment of acute GVHD is allowed, however, ECP must have occurred > 4 weeks prior to Cycle 1 Day 1.
 
 
Key Exclusion Criteria:
 
 
• Subjects with score 3 lung GVHD or biopsy-proven bronchiolitis obliterans.
 
• Uncontrolled manifestations of acute GVHD.
 
• Received prior JAK inhibitor therapy for any indication <math>\leq</math> 4 weeks prior to Cycle 1 Day 1.
 
• Received any previous systemic treatment for chronic GVHD.
 
• Relapsed or progressive malignant disease or any post-transplant lymphoproliferative disease
 
• Treatment with any other investigational agent, device, or procedure, within 30 days of enrollment
 
• Inability swallow food or any condition of the upper gastrointestinal tract that precludes administration of oral medications
 
• Uncontrolled infections
 

Study Product, Dose, Route, Regimen
	
Treatment will initiate at 200 mg daily of itacitinib (Cohort 1). If unacceptably high DLTs are observed, the itacitinib dose can be sequentially reduced to 100 mg oral daily (Cohort -1) and then 100 mg oral every other day (Cohort -2). Patients in Part 1 who do not experience a DLT are permitted to continue treatment at their initial dose.
 
ECP will be given at a frequency of twice weekly for 8 weeks followed by a standard taper schedule as per study protocol if there is a response.

Duration of administration
	
Treatment with itacitinib will be administered continuously until the end of week 24 or until treatment discontinuation criteria is met. Patients with PR or better may continue itacitinib for up to 1 year.

Reference therapy	Reference therapy is systemic steroids. We are comparing historical response rates to high dose steroids.

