## 4 STUDY DESIGN

### 4.1 Description

This is an open-label, Phase II trial designed to assess the recommended phase 2 dose (RP2D) of itacitinib in combination ECP and efficacy of the combination after 24 weeks of therapy. The trial will consist of two parts: Part One will assess the RP2D. For dose-finding purposes, the DLT evaluation period will be defined as the time from the first dose of itacitinib lead-in (7-day lead-in) to the last day of cycle one combination therapy (cycle one day 28). Part Two will further describe and characterize the safety and efficacy of the regimen. The RP2D will be determined by a 3+3 dose de-escalation design. Should dose level one be deemed intolerable, enrollment will proceed at dose level -1. The RP2D will be affirmed according to the rules of the 3+3 dose de-escalation scheme (Section 4.2). Once an RP2D has been confirmed, Part 2 will open as an expansion cohort. Safety will be monitored during the trial as described in Section 11.3.

All eligible patients will begin study therapy with approximately a week lead-in of itacitinib monotherapy. After completing the itacitinib lead-in, combination treatment will begin in 28-day cycles. After eight weeks of combination therapy, patients will begin an ECP taper and continue on itacitinib for a total of 6 cycles. Patients achieving PR or better may

continue on itacitinib for up to 1 year. Patients will remain on study therapy as long as treatment discontinuation criteria are not met.

Prednisone dose (or prednisone equivalent) at  $\leq 0.25$  mg/kg/d for treatment of GVHD progressing or not sufficiently responding to study treatment will be allowed, at the discretion of the treating investigator and with approval of the PI, while the participant is on study treatment. Addition of prednisone dose (or prednisone equivalent) at  $\leq 0.25$  mg/kg/d will not be considered as failure of the primary endpoint. Prednisone doses (or prednisone equivalent) of  $> 0.25$  mg/kg/d but  $\leq 0.5$  mg/kg/d for more than 8 weeks or  $> 0.5$  mg/kg/d once will count as a failure of the primary endpoint, but the participant will be allowed to remain on the treatment period of the study. If the participant requires any systemic immunosuppression besides prednisone (i.e., ibrutinib, ruxolitinib, etc.), the participant will be withdrawn from study treatment but remain on study for follow-up.

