### 5.1 Inclusion Criteria

**Yes/No (Response of "no" = patient ineligible)**

- 5.1.1 \_\_\_\_\_ Male or female subject aged  $\geq 18$  years.
- 5.1.2 \_\_\_\_\_ Active, clinically diagnosed, moderate or severe chronic GVHD as defined by the NIH Consensus Development Project Criteria (See Appendix 2).
- 5.1.3 \_\_\_\_\_ History of an allogeneic hematopoietic cell transplant with any conditioning regimen, donor, or graft source.
- 5.1.4 \_\_\_\_\_ Need for systemic treatment for chronic GVHD as assessed by the treating investigator.
- 5.1.5 \_\_\_\_\_ No previous systemic treatment for chronic GVHD.
- Note: Participants may be receiving immunosuppressants for the prophylaxis or treatment of acute GVHD, but these medications must have been stable for at least 2 weeks prior to the initiation of study therapy. Prednisone dose (or its equivalent) should be at doses of  $\leq 0.25$  mg/kg/d for at least 2 weeks prior to the initiation of study therapy.
- Topical or inhaled treatments for chronic GVHD are allowed. Any prior ECP treatments for the management of acute GVHD must have occurred  $> 4$  weeks prior to the initiation of itacitinib treatment.
- 5.1.6 \_\_\_\_\_ Able to swallow and retain oral medication.
- 5.1.7 \_\_\_\_\_ Life expectancy  $> 24$  weeks.
- 5.1.8 \_\_\_\_\_ Karnofsky performance status  $\geq 60$
- 5.1.9 \_\_\_\_\_ Evidence of myeloid and platelet engraftment:
- Absolute neutrophil count  $\geq 1000/\text{mcL}$
  - Platelet count  $\geq 25,000/\text{mcL}$

Note: Use of growth factors and transfusion support is allowed during the study; however, growth factors and transfusion support to reach a minimum ANC or

platelet count for inclusion are not allowed within the 7 days before the screening laboratory assessment.

**5.1.10** \_\_\_\_\_ Adequate organ function as defined as:

- **Hepatic:**
  - Total bilirubin  $\leq 2$  mg/dL
  - AST(SGOT)/ALT(SGPT)  $\leq 2.5 \times$  institutional ULN (unless of non-hepatic origin). AST/ALT  $\leq 5 \times$  ULN is acceptable if associated with chronic GVHD.
- **Renal:**
  - eGFR  $\geq 30$  mL/min/1.73 m^2 as calculated using the Modification of Diet in Renal Disease formula or by the Cockcroft-Gault formula:
    - Males:  $\frac{(140 - \text{age}) \times \text{weight}[\text{kg}]}{\text{serum creatinine} \left[ \frac{\text{mg}}{\text{dL}} \right] \times 72}$

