## 12 STATISTICAL CONSIDERATIONS

### 12.1 Sample Size Determination

#### Part 1

Part 1 has a maximum of 18 patients. Part 1 has a 3+3 dose de-escalation design with 3 doses and a maximum of 6 patients per dose.

#### Part 2

The sample size for Part 2 is 16-46 patients with 6 patients carried over from Part 1 at the RP2D. Simon’s optimal two-stage design will be used in Part 2. The primary outcome is the overall response rate (CR + PR) at 24 weeks. Withdrawal or progression prior to 24 weeks or missing 24-week assessment will be considered non-response. After the first 16 patients treated at the RP2D complete 24 weeks of therapy or meet treatment discontinuation criteria, enrollment will be put on hold and an interim analysis will be conducted. This study treatment will be considered promising if the overall response rate at 24 weeks is  $\geq 60\%$  and unacceptable if the overall response rate at 24 weeks is  $\leq 40\%$ . 50% is the reported best overall response rate of current first-line therapy with high-dose steroids. The null hypothesis that the true response rate is  $\leq 40\%$  will be tested against a one-sided alternative.

In the first stage of the dose-expansion study, 16 patients will be accrued and followed through the first 24 weeks of treatment. Of those 16 patients, 6 patients will be carried over from Part 1 at the RP2D. In recognition of a potential accrual pause of at least 24 weeks if all 16 patients are required to complete six months of combination therapy, we will permit enrollment of an additional 3 patients (20%) after the first 10 eligible patients in the first stage of the dose-expansion study are enrolled if no more than 5 of 16 patients have experienced treatment failure (i.e. addition of secondary systemic therapy or disease relapse or death) by the end of week 12 of treatment. If there are 7 or fewer responses in the first 16 patients enrolled, the study will be stopped. Otherwise, 30 additional patients

will be accrued for a total of 46. The null hypothesis will be rejected if 24 or more responses are observed in 46 patients. This design yields a type I error rate of 0.0486 and a power of 80% when the true response rate is  $\geq 60\%$ .

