### **12.2.3 Evaluable for response**

Patients who have received at least two weeks of combined ECP and itacitinib administration will be evaluable for efficacy endpoints.

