## Efficacy

- Overall response rate at 1-year as determined by the NIH Consensus Development Project Criteria, without secondary systemic immunosuppression and no recurrent malignancy or death
- Failure Free Survival (FFS) at 24 weeks and 1-year as defined as the time from the initiation of study therapy until treatment failure defined as the initiation of secondary therapy for chronic GVHD, malignancy relapse, or death from any cause.
- The proportion of patients who have withdrawn all immunosuppressants at 1-year.
- Overall response rate at 24 weeks, as determined by the NIH Consensus Development Project Criteria, stratified by concurrent prednisone (or equivalence) use: 0 mg/kg/d,  $\leq 0.25$ mg/kg/d, and  $> 0.25$ mg/kg/d.
- The mean cumulative prednisone dose used at 24 weeks.
- Organ-specific response rates at 24 weeks and 1-year as determined by the NIH Consensus Development Project Criteria.
- Change in NIH global score of chronic GVHD from baseline to 24 weeks and 1-year after the initiation of the protocol therapy. The NIH global score will be defined by using the NIH consensus criteria for the assessment of chronic GVHD severity.
- Duration of response (DOR), defined as the interval between the date of initial documentation of a response (PR or better), and the time of progression from the best response, the start of a new therapy for cGVHD (including corticosteroids), or death from any cause.
- Provider-reported chronic GVHD severity at baseline, 24 weeks, and 1-year.
- Patient-reported chronic GVHD severity at baseline, 24 weeks, and 1-year.
- 24 week and 1-year non-relapse mortality (NRM) defined as the proportion of participants who died due to causes other than a relapse of their primary hematologic disease.
- Relapse rate (RR) of malignant and non-malignant hematologic diseases, defined as the proportion of participants whose underlying disease relapses at 24 weeks and 1-year.
- Overall survival (OS) as defined as the time from the initiation of study therapy until death from any cause at 24 weeks and 1 year.

Observed proportions and exact binomial confidence intervals will be reported for binary endpoints with no censored events. These may include withdrawal from immunosuppressants at 1-year, the overall response at 24 weeks stratified by current prednisone use (0 mg/kg/d,  $\leq 0.25$ mg/kg/d, and  $> 0.25$ mg/kg/d.), the overall response at 1 year, organ-specific response at 24 weeks and 1 year, no recurrent malignancy, no

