addition of new systemic treatment for chronic GVHD, and use of prednisone dose (or its equivalent) of  $\leq 0.5$  mg/kg/d at 24 weeks. Kaplan-Meier methods will be used for these binary endpoints if there are censored events. Kaplan –Meier methods and associated confidence intervals will be used for survival endpoints (FFS and OS). NRM and RR will be treated as competing risks and analyzed by computing nonparametric subdistribution functions. The minimum, maximum, mean, and median value along with interquartile range will be reported for continuous and ordered categorical endpoints (NIH global score of chronic GVHD, provider, and patient-reported GVHD severity). Change in continuous or ordered categorical endpoints (NIH global score of chronic GVHD, provider, and patient-reported GVHD severity) will be analyzed using paired Wilcoxon tests. The minimum, maximum, mean, and median cumulative prednisone dose at 24 weeks will be reported, along with the interquartile range.

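### The paired Wilcoxon tests of change in NIH global score and GVHD severity have no rule for deaths, missing scores or scores after secondary therapy, so an analysis of assessed patients can lean toward improvement

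*Combined protocol and SAP*

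**What the plan says.** Section 12.4.2 (Efficacy) lists as a secondary endpoint "Change in NIH global score of chronic GVHD from baseline to 24 weeks and 1-year after the initiation of the protocol therapy", together with provider- and patient-reported severity at baseline, 24 weeks and 1 year. Changes in these measures "will be analyzed using paired Wilcoxon tests". No significance level, sidedness, visit window or missing-data rule is given for these tests.

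The analysis set comes from section 12.2.3: "Patients who have received at least two weeks of combined ECP and itacitinib administration will be evaluable for efficacy endpoints".

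The only missing-data rule in the statistical section belongs to the 24-week response endpoint (section 12.1, repeated in 12.4.1): "Withdrawal or progression prior to 24 weeks or missing 24-week assessment will be considered non-response".

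Several passages keep failures under observation:
- Under section 4.1, prednisone use above the stated limits "will count as a failure of the primary endpoint, but the participant will be allowed to remain on the treatment period of the study".
- Under the same section, if other systemic immunosuppression is needed, "the participant will be withdrawn from study treatment but remain on study for follow-up".
- Table 7 schedules a chronic GVHD assessment at the progression, end-of-treatment and follow-up visits.
- Section 9.5 follows all patients every 12 weeks for 12 months after they leave treatment.

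**The concern.** A signed-rank test needs a baseline and a later value from the same patient. A patient who died before 24 weeks or 1 year has no later value and cannot enter. A patient who is alive but unassessed is omitted too, and section 12.2.3 removes anyone with under two weeks of combined therapy. If loss goes with worsening, the patients who remain look better than the patients who were treated. In a single-arm trial no control group shares that bias.

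For failures who are still seen, the gap is different. Nothing says whether a score taken after another systemic agent counts toward itacitinib plus ECP, or which off-treatment visit stands for 24 weeks or 1 year.

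At stake is a p-value for improvement that could be read as applying to everyone treated, next to a primary endpoint that handles the same patients in the opposite way.

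**Working it through.** **1. The plan's own figures.** The only operating characteristics stated for an efficacy analysis are those of the Simon design. Rejection probability = Σ over x = 8 to 16 of P(X = x; 16, p) × P(Y ≥ 24 − x; 30, p). At p = 0.40 this is 0.0486 and at p = 0.60 it is 0.8006, matching the stated 0.0486 and 80%. Nothing comparable is stated for the Wilcoxon tests.

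**2. Illustration: assumptions.** N = 46 is the Part 2 maximum. The rest is assumed: 40% improve (four-fifths by 1 point, one-fifth by 2), 30% are unchanged, 30% worsen by 1 point, and the test is two-sided at 0.05. The 40% borrows the protocol's unacceptable response rate, although response and change in global score are different measures.

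**3. Effect on the mean change.**
- All assessed: −0.40 × (0.8 × 1 + 0.2 × 2) + 0.30 × 1 = −0.48 + 0.30 = −0.18.
- One in six of the worsened lost (0.30 × 46 / 6 = 2.3 patients): (−0.48 + 0.25) / 0.95 = −0.24.
- Half of the worsened lost (0.30 × 46 / 2 = 6.9 patients): (−0.48 + 0.15) / 0.85 = −0.39.

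**4. Chance of a significant improvement (simulation).**

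| Worsened patients lost | Assessed patients only | Lost patients given worst rank |
|---|---|---|
| None | about 24% | about 24% |
| One in six | 38 to 39% | about 11% |
| Half | 76 to 77% | about 2% |

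The 24% is not a false-positive rate, because the assumed net change is a small true improvement. If every improver gains exactly 1 point, the assessed-only figures are about 12%, 25% and 66%. If 15% of patients are lost at random instead, the figure is about 20%: some power goes, but no tilt appears.

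**5. No true net change (N = 46, symmetric changes).** Assessed-only chance of significant improvement, where the nominal one-direction rate is 2.5%:
- loss at random: 2 to 3%;
- 2 lost (5.3%): 5 to 8%;
- 9 lost (20%): 18 to 59%;
- 14 lost (30.5%): 29 to 88%.

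In each range the low end has loss correlated 0.5 with worsening, and the high end loses exactly the worst patients. Worst-rank scoring gives at most about 2% with 2 lost and 0% with 9 or 14 lost. The 5.3% is the share with fatal events and the 30.5% the share discontinuing treatment in the chronic GVHD study summarised in section 3.1.6. Neither measures missed assessments in this trial.

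**6. Visit timing.** A patient who stops at week 24 has section 9.5 visits at about weeks 36, 48 and 60, each ±7 days. Week 52 falls in none of those windows. A patient who stops at week 8 is seen at about weeks 20, 32, 44 and 56, which miss both week 24 and week 52.

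**7. The proposed summary in the same illustration.** Improved patients number 0.40 × 46 = 18.4. Over all treated, the proportion is 18.4 / 46 = 40% however many of the worsened are lost. Over assessed patients with half of the worsened lost, it is 18.4 / (46 − 6.9) = 47%.

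**The case against.** The strongest reply is that failures do not simply vanish. Prednisone failures may stay on treatment, patients who need other agents stay on study, and GVHD assessments continue off treatment. This stands. It limits certain omission to deaths, to patients with under two weeks of combined therapy, and to patients who are in fact unassessed. A reader might infer that all failures drop out; the documents contradict that.

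A reader might also infer that the 1-year sample is chosen for having improved, because "Patients with PR or better may continue itacitinib for up to 1 year". That sentence limits who may continue the drug. Section 12.4.2 does not restrict the 1-year analysis to patients on treatment, and section 9.5 keeps the others under observation.

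A third inference is that a significant result is close to certain. It is not. With loss of about 5% and no net change, the chance is 5 to 8%. A model in which no patient worsens does give near-certain significance at 40% improving, but it does so whether failures are lost or kept as unchanged, so it says nothing about missing data. The tilt needs lost patients to be worse than those who remain, which is plausible but assumed here.

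Finally, these tests carry no success rule. Deaths, relapse and secondary therapy are reported through failure-free survival, overall survival, non-relapse mortality and relapse rate, and the response endpoint already has a responder proportion. This lowers the severity. It does not correct a change score and p-value that leave those patients out.

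**Conclusion.** The gap is real: the paired tests have no rule for deaths, missing scores or scores after secondary therapy, and as written they can use only patients with both values. The direction is toward improvement when the lost patients are the worse ones. The size is not fixed by the documents. In the illustration the chance of significance rises from about 24% to 38 to 39% with roughly two worsened patients lost, and to 76 to 77% with roughly seven lost. Random loss produces no tilt. All response, worsening and loss rates are assumptions. On a three-grade scale a patient already severe cannot record a worse grade, so the one-point worsening is a simplification.

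Severity is minor. This is a cheap improvement to a secondary analysis with no decision attached, and it does not threaten the primary conclusion.

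**What to change.** In section 12.4.2:
- At 24 weeks and 1 year, report the proportion of all treated patients whose NIH global score improved by at least one category, with an exact binomial confidence interval. Count death, relapse, secondary systemic therapy (as defined for the primary endpoint) or a missing assessment as not improved. State that the denominator is all treated patients and not the section 12.2.3 set.
- Keep the paired Wilcoxon tests for all three measures as descriptive, labelled as patients assessed, with the numbers assessed and omitted and the reasons. State how scores after secondary therapy are used.
- Add a worst-rank Wilcoxon as a sensitivity analysis. It ranks a lost patient below every observed patient, so it is deliberately conservative.
- State which visit, with what window, counts as 24 weeks and 1 year for patients off treatment. Reconcile section 9.3 (6 months of follow-up for GVHD progression after the end-of-treatment visit) with section 9.5 (12 months), since the length decides whether early stoppers reach 1 year.

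The descriptive label has a second reason: entry requires "Active, clinically diagnosed, moderate or severe chronic GVHD as defined by the NIH Consensus Development Project Criteria", so some apparent improvement may be regression to the mean. The proposed proportion does not remove that.

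The cost is SAP wording and one extra table, with no added visits unless the visit rule requires one. The result will be coarser and somewhat less favourable.

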### **12.4.3 Exploratory Endpoint Analysis**

#### **Duration of Response (DOR)**

Duration of response (DOR) is defined as the interval between the date of initial documentation of a response (PR or better), and the time of progression from the best response, the start of a new therapy for cGVHD (including corticosteroids), or death from any cause. DOR will be summarized for all responders. Non-responders will be excluded from the analysis of DOR. The median duration of response will be estimated using Kaplan-Meier methodology.

#### **Patient-Reported Outcomes**

As assessed by the change in QOL-SF-36-v2 questionnaire, Lee Chronic GVHD Symptom Scale, and Activity Measure for Post Acute Care (AM-PAC) Basic Mobility Outpatient Routine Short Form scores at 24 weeks.

#### **Pharmacodynamics**

The extent of inhibition of JAK1 and STAT phosphorylation in response to relevant cytokines, when administered in combination with ECP in subjects with chronic GVHD.

#### **Biomarkers**

To assess the changes in T-cell subsets, B cell population, cytokine expression, and other biomarkers of chronic GVHD.

#### **Socioeconomic Factors**

To evaluate any changes in socioeconomic status (i.e., changes in residence, annual income, insurance type, employment status) with cGVHD outcomes and protocol non-compliance.

## 13 REGISTRATION GUIDELINES

**Study-related screening procedures can only begin once the patient has signed a consent form.**

**Patients must meet all of the eligibility requirements listed in Section 5 prior to registration.**

**Patients must be registered before receiving any study treatment and must begin treatment within five working days after registration.**

To register eligible patients on study, complete a Clinical Trials Office Patient Registration Form and submit to [[contact]](mailto:[contact]). To register a patient at a site outside of HCI, complete a Clinical Trials Office Patient Registration Form, and submit to [[contact]](mailto:[contact]).

